Objective 2: The study population for Objective 2 is clinic staff from all clinics participating in UP FOR IT. Our partners at the Kentucky Regional Extension Cooperative have identified partner clinics in two healthcare systems in Kentucky (Big Sandy and Penny Royal, see LOS). We anticipate having between 5-6 participants at each of the 11 clinics that are participating in the intervention. This will yield a total sample size for Objective 2 of n=65 clinic staff. There are no additional inclusion/exclusion criteria beyond employment at a participating clinic. The proposed start date for enrolling these participants is October 1, 2022 and the proposed end date is November 30, 2022.

Objective 3: We will recruit key informants from two stakeholder groups: 1) clinic staff and clinicians who participated in the UP FOR IT intervention and 2) KDPH DSMES providers whose DSMES service catchment area included those clinical practices participating in UP FOR IT. Kentucky Regional Extension Cooperative staff will recruit two stakeholders from each of the 11 participating clinical practices from two healthcare systems (N=22) for surveys/key informant interviews. KDPH will aid in recruiting two DSMES providers from the regions where UP FOR IT took place. This will yield a total sample size for Objective 3 of 13 (n=22 clinic staff and n=2 DSMES providers). There are no additional inclusion/exclusion criteria beyond participation in UP FOR IT. The proposed start date for enrolling these participants is October 1, 2024 and the proposed end date is December 1, 2024.

Attachments

Indicate the targeted/planned enrollment of the following members of minority groups and their subpopulations. Possible demographic sources: [Census Regional Analyst Edition](#), [Kentucky Race/Ethnic Table](#), [Kentucky Population Data](#).

(Please note: The IRB will expect this information to be reported at Continuation Review time for Pre-2019 FDA-regulated Expedited review and Full review applications):

Participant Demographics

Cisgender Man 	Cisgender Woman 	TGNB/TGE 	Unknown/Not Reported
---	---	--	----------------------

American Indian/Alaskan Native:			
Asian:			
Black/African American:			
Latinx:			

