In this study, we propose implementing health information technology, including automated patient identification and bidirectional secure messaging between clinicians and DSMES providers, and using practice facilitation to address referral barriers and increase clinician awareness and motivation. We have partnered with KDPH (statewide DSMES provider), Kentucky Regional Extension Cooperative (KY-REC, practice facilitation partner), Kentucky Health Information Exchange (health information technology (HIT) partner) and two healthcare systems in rural Kentucky. Our proposal builds on a diabetes quality improvement collaborative facilitated by KY-REC and KDPH that demonstrated increased DSMES utilization. We will use a rigorous study design to evaluate implementation processes and effectiveness by testing the hypothesis that patient identification and referral strategies, bidirectional linkages between clinics and DSMES providers, and primary care clinician engagement will increase DSMES utilization through the following objectives:

Objective 1 – Planning: To use an established implementation science framework (PRISM) to identify determinants of DSMES uptake in Kentucky by interviewing previous DSMES quality improvement collaborative stakeholders, and to adapt the previous intervention using implementation mapping to connect stakeholder determinants to intervention strategies and outcomes.

Objective 2 – Implementation: To implement an intervention comprised of health information technology and a practice facilitation collaborative with two healthcare systems in rural Kentucky to increase DSMES referral rates and gather preliminary data for the planned R01 study.

Objective 3 – Evaluation: To evaluate the pragmatic implementability of the intervention by assessing the feasibility, acceptability, and sustainability of the intervention via stakeholder and participant survey, administrative and interview data.

Study Design

Describe and explain the study design (e.g., observational, secondary analysis, single/double blind, parallel, crossover, deception, etc.).

- **Clinical Research:** Indicate whether subjects will be randomized and whether subjects will receive any placebo.
- **Community-Based Participatory Research:** If you are conducting [community-based participatory research \(CBPR\)](#), describe strategies for involvement of community members in the design and implementation of the study, and dissemination of results from the study.

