Objective 2 is a pragmatic cluster randomized trial. We have partnered with two rural healthcare systems (one in eastern Kentucky and one in Western Kentucky) for this study. Two clinics from each system will be randomized to participate in the intervention (4 total intervention sites) and the remaining clinics will serve as the control sites. The intervention consists of health information technology (including an automated patient identification system and bidirectional e-referral system connecting clinics to the DSMES providers) and a practice facilitation collaborative. The collaborative is a structured, facilitated process that brings together teams from different organizations to learn from one another. The collaborative utilizes the Model for Improvement, a quality improvement approach designed by the Institute for Healthcare Improvement that uses rapid cycle quality improvement – repeated PDSA (plan do study act) cycles meant to identify care quality barriers and rapidly implement and measure change. Teams from intervention clinics will apply this quality improvement strategy to identify and address quality gaps in diabetes care and DSMES utilization at their clinics. Practice facilitators on the study team will provide individualized coaching (practice facilitation) to clinics in the intervention arm of the study. We will assess the effect of the interventions on DSMES referrals (primary outcome), by comparing rates of referrals between intervention and control clinics (clinics within the healthcare system not randomized to the intervention). Secondary outcomes include DSMES attendance, patient satisfaction and diabetes knowledge, A1c control, and intervention feasibility and acceptability.

Objective 3 involves surveys and interviews with clinic staff that participated in the intervention and DSMES providers from the geographic areas where the intervention took place. Interviews will be conducted via phone and audio will be recorded. The goal of Objective 3 is to understand how the various implementation strategies embedded within the practice facilitation collaborative and clinical context influenced DSMES uptake to inform future refinement for program replication and scale-up.

Attachments

Subject Recruitment Methods & Advertising

Describe how the study team will identify and recruit subjects. Please consider the following items and provide additional information as needed so that the IRB can follow each step of the recruitment process.

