Objective 3: Kentucky Regional Extension Cooperative staff will recruit two stakeholders from each of the 11 participating clinical practices from two healthcare systems to participate in surveys and a key informant interview. KDPH will aid in recruiting two DSMES providers from the regions where UP FOR IT took place.

n/a

Attachments

Attach Type	File Name
Advertising	DSMES AIM 1 Recruitment Email_11.1.22.pdf

Research Procedures

Describe how the research will be conducted.

- What experience will study participants have?
- What will study participants be expected to do?
- How long will the study last?
- Outline the schedule and timing of study procedures.
- Provide visit-by-visit listing of all procedures that will take place.
- Identify all procedures that will be carried out with each group of participants.
- Describe deception and debrief procedures if deception is involved.

Differentiate between procedures that involve standard/routine clinical care and those that will be performed specifically for this research project. List medications that are explicitly forbidden or permitted during study participation.

Objective 1: A study team member not involved in the first DLC in will conduct the key informant interviews to minimize stakeholder and interviewer bias. Interview guides are attached. Interviews will happen via telephone and will be recorded; we will transcribe interviews for analysis. Based on these findings, key stakeholders and members of the research team will utilize the PRISM Assessment Tool (attached) a group-based action planning approach, to assess and address contextual domains for the implementation of an evidence-based intervention (DSMES) and select or adapt strategies that address key areas identified as being important and showing low alignment with the local context.

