Objective 3: We will use the same qualitative methods described in Objective 1 to analyze PRISM concepts, such as fidelity to the core components of the PFC and any necessary adaptations to either the PFC or to the selected implementation strategies (using the PRISM Assessment Tool, attached). To do so, we will conduct midpoint evaluations with program staff and other key stakeholders six months after initial program rollout as well as immediately upon conclusion. We will again use the PRISM survey and interview guide (see attachments: PRISM Assessment Tool and PRISM Interview Guide) to assess PRISM domains and provide context to understand the reasoning for any differences that exist between pre-implementation (i.e., anticipated) and midstream (i.e., unanticipated) adaptations. Two implementation scientists (Drs. [name] and [name]) with significant qualitative research experience will independently code the data and map responses to PRISM domains. To better understand the context and reasoning for implementation strategies, we will collect monthly reports from the learning collaborative teams; following the recommendations of Proctor and colleagues, we will ask the teams to (1) name, (2) define, and (3) operationalize (actor, action, target, temporality, dose, intended implementation outcome affected, and justification) each implementation strategy using a simple template document. These reports will help contextualize qualitative findings with respect to program adaptations. Finally, upon program conclusion, we will assess the implementation outcomes of feasibility, acceptability, and appropriateness on each implementation strategy as well as the intervention itself. To do so, we will ask program staff and other key stakeholders to complete a brief, 12-item psychometrically validated survey consisting of three scales measuring feasibility, acceptability, and appropriateness; for each scale, scores are summed and averaged for each individual scale, with higher scores indicating more favorable implementation outcomes (Attached: Triple P System Implementation Outcomes). These data will provide summative information about which strategies were effective at increasing DSMES utilization within the specific program setting. Taken together, these data will help refine any additional necessary adaptations and selection/refinement of implementation strategies for future scale-up activities.

Attachments

Data Collection & Research Materials

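### The facilitation partner recruits two staff per clinic for the Objective 3 survey with no stated selection rule, so the feasibility and acceptability ratings are at risk of favourable selection

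*Combined protocol and SAP*

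**What the plan says.** Under Study Population, Objective 3, the plan states that "Kentucky Regional Extension Cooperative staff will recruit two stakeholders from each of the 11 participating clinical practices", and Subject Recruitment Methods & Advertising repeats this. Participation in the intervention is the only criterion. Two DSMES providers are added, recruited with the state health department's help. The Objective 2 text in Study Population expects 5–6 participants at each clinic.

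The Objectives section identifies the recruiting organisation as "Kentucky Regional Extension Cooperative (KY-REC, practice facilitation partner". Study Design says: "Practice facilitators on the study team will provide individualized coaching (practice facilitation) to clinics in the intervention arm of the study". The same section lists the outcomes at issue: "Secondary outcomes include DSMES attendance, patient satisfaction and diabetes knowledge, A1c control, and intervention feasibility and acceptability". The Data and Safety Monitoring Plan gives feasibility and acceptability as a purpose of the pilot.

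On who fills in the rating instrument, Research Procedures, Objective 3, says "we will ask program staff and other key stakeholders to complete a brief, 12-item psychometrically validated survey". Objective 3 as a whole is to be assessed "via stakeholder and participant survey, administrative and interview data".

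Two safeguards are stated. Under Research Procedures, Objective 1, a team member who was not part of the first collaborative "will conduct the key informant interviews to minimize stakeholder and interviewer bias". Under Records, Privacy, and Confidentiality, all surveys are de-identified.

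**The concern.** An organisation that delivers an intervention is poorly placed to decide who is asked whether that intervention was acceptable. The people easiest to recruit are often those who engaged most, and they may also rate the programme best. With two of 5–6 people needed per clinic and no roster, random draw, role quota or survey of all participants described, nothing in the plan limits that link.

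The stated safeguards act elsewhere. An independent interviewer governs who asks the questions. De-identification may make answers franker. Neither governs who is asked.

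At stake is how far the acceptability and feasibility scores can be read as the view of participating staff. The primary outcome, DSMES referrals, comes from clinic record reports and is not affected.

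**Working it through.** **Inputs from the documents**
- Recruits per clinic: 2. Clinics: 11 (Study Population, Objective 3).
- Participants per clinic: 5–6 (Study Population, Objective 2).
- Intervention and control clinics: 4 and 7 (Data and Safety Monitoring Plan, sample size justification).
- DSMES providers: 2.
- Not given: the number of program staff who rate, the SD of the scores, and any information on how recruitment relates to rating.

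**1. The plan's own counts.** 2 × 11 = 22 clinic staff, as printed. 22 + 2 = 24, but the same sentence prints a total of 13. The Objective 1 total is also 13 (10 + 3). The point here does not depend on the 13, but that figure needs correcting.

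**2. Who can rate the facilitation.** Intervention clinics: 4 × 2 = 8 recruits. Control clinics: 7 × 2 = 14 recruits, who would have no facilitation to rate. Objective 3 describes its clinic respondents as intervention participants yet recruits from all 11 clinics. These two statements must be reconciled.

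**3. Room for selection.** Two of 5 is 40% of the pool, and two of 6 is 33%. Leaving aside program staff, the partner recruits 22/24 = 92% of the listed respondents, or 8/10 = 80% if only the intervention clinics and the two providers rate.

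**4. Size of a possible shift.** Assume that ratings within a clinic are independent and normal with SD 1. Assume also that the two people recruited rank highest on something correlated ρ with their rating. The expected shift in the recruits' mean is then

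shift = ρ × E(mean of the top 2 of n).

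Simulation with 1,000,000 draws gives E = 0.83 for n = 5 and 0.95 for n = 6.

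| Assumed ρ | Shift, within-clinic SD (n = 5 to n = 6) |
|---|---|
| 0 | 0 |
| 0.25 | 0.21–0.24 |
| 0.5 | 0.41–0.48 |
| 1 (always the two most favourable) | 0.83–0.95 |

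The values of ρ are assumptions; the documents support none of them over another.

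**5. Scale.** With independent raters, the standard error of a mean of 8 is 1/√8 = 0.35 SD, and of 22 is 1/√22 = 0.21 SD. At ρ = 0.5 the shift would exceed the sampling error of the 8 intervention-clinic raters. At ρ = 0.25 it would not.

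**6. Dilution.** If the two providers are pooled in unshifted, the recruits carry 8/10 of the weight. At ρ = 0.5 the shift in the pooled mean is 0.8 × 0.41 to 0.8 × 0.48 = 0.33–0.38 SD. The ceiling is 0.8 × 0.83 to 0.8 × 0.95 = 0.66–0.76 SD. Program-staff ratings would change this further, by an amount that cannot be computed without their number.

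**The case against.** The strongest reply is that the documents say only that the partner recruits. They do not say that it picks favourable people, or that a clinic's own facilitator makes the approach. They contain no data on bias, so the shift may be zero. That stands. A reader might infer that the secondary outcome is biased upward as a matter of fact, and the text supports only an unguarded risk.

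A reader might also infer that the two recruits per clinic are the only raters. They are not: program staff complete the 12-item survey, DSMES providers are included, and administrative data are named as a source. This limits the recruits' weight. It does not remove the concern, because program staff who helped deliver the intervention would themselves be interested raters.

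A third tempting reading is that the plan guarded against this bias in Objective 1 and then dropped the guard. It did not. Objective 1 uses the same recruiting organisation and the same two per clinic, also without a rule, and its safeguard concerns only the interviewer.

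A fourth is that the acceptability scores will justify the planned R01. The Objectives section ties the R01 preliminary data to Objective 2, while Objective 3 is directed at refinement and scale-up. Acceptability is listed among the Objective 2 secondary outcomes, so a link can be argued, but no section states it.

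Finally, these people are called key informants, and purposive choice of informants is normal for interviews. That also stands. The point therefore concerns the survey scores and not the choice of interviewees.

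**Conclusion.** The point holds as a risk of favourable selection in the survey ratings of feasibility and acceptability. It rests on four facts in the documents: the facilitation partner recruits, it needs two of 5–6 people per clinic, no selection rule is given, and the stated safeguards do not reach this step. Upward is the plausible direction, but this is a judgement.

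The size is unknown. It runs from 0 to a ceiling of 0.83–0.95 within-clinic SD among the recruited staff, with 0.41–0.48 SD under the assumed correlation of 0.5. These figures assume roughly normal ratings. They cannot be turned into scale points because no SD is given, and on a bounded scale where most people score high the shift would be smaller. About 8 of the 22 recruits can rate the facilitation at all. The point is minor: it bears on how one secondary outcome is read and is cheap to fix.

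**What to change.** In Study Population (Objective 3), Subject Recruitment Methods & Advertising (Objective 3) and Research Procedures (Objective 3):

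- Have the partner supply only the roster of enrolled participants. Since facilitators are on the study team, name a team member outside the partner to send the survey.
- Send the 12-item REDCap survey to every enrolled participant at the 4 intervention clinics: 4 × 5 to 4 × 6 = 20–24 people planned. This removes the selection step.
- Report respondents over eligible participants for each clinic, and report program-staff ratings separately from clinic-staff ratings.
- Reconcile the 11-clinic recruitment with the 4 clinics that receive facilitation, and correct the Objective 3 total.

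Interviewees may still be chosen purposively.

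The cost is small: the survey is already electronic and no new staff are needed. The downside is that response may be slightly lower without a personal request from the partner.

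Timing may prevent this. The Objective 3 enrolment window was October 1 to December 1, 2024, and the Protocol Changes log shows that the study was marked closed to new enrolment on December 18, 2024. If data collection is complete, report how the respondents were selected and the coverage per clinic, and state this as a limitation. Use the roster-based survey in any later scale-up.

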- Use one of the attachment buttons in this section or under the Additional Information section to include supplemental information with your application. During the document upload process, you will be able to provide a brief description of the attachment.

Background

Include a brief review of existing literature in the area of your research. You should identify gaps in knowledge that should be addressed and explain how your research will address those gaps or contribute to existing knowledge in this area. For interventional research, search PubMed and ClinicalTrials.gov for duplicative ongoing and completed trials with same condition and intervention(s).

Rates of diabetes in Kentucky are among the highest in the United States (US) and rural areas of Kentucky experience even higher rates of diabetes and diabetes-related complications. From 2000 to 2020, the prevalence of diabetes in Kentucky more than doubled from 6.5% to 13.3%. Kentucky has the 7th highest prevalence of diabetes and the 4th highest rate of diabetes mortality in the US. Within Kentucky, rural areas face an even higher burden of diabetes and its related complications. While the statewide prevalence of diabetes is already among the highest in the nation, in Appalachia, the prevalence of diabetes exceeds 20% of the adult population.

Diabetes self-management education and support (DSMES) is an integral part of diabetes management. It is associated with a range of improvements in diabetes-related outcomes and reduction in diabetes-related healthcare costs, yet it is vastly underutilized. DSMES is an evidence-based service delivered by a credentialed diabetes educator that teaches people with diabetes how to effectively self-manage their disease. DSMES effectively provides individuals necessary skills to manage their diabetes; it is linked to better glycemic control, a reduction in mortality, and improved quality of life. In addition to its clinical effectiveness, DSMES is cost-effective and reduces the overall cost of care for people with diabetes. Driving its cost-effectiveness, DSMES is associated with better alignment with best practice diabetes treatment, lower claims costs, increased medication adherence, and decreased spending on inpatient care. However, despite strong evidence supporting DSMES and clear guidelines from the American Diabetes Association (ADA) recommending its use and specifying times when DSMES should be offered,¹² DSMES is significantly underutilized. Recent estimates suggest that <10% of individuals with diagnosed diabetes have used DSMES. Further, studies suggest that rates of DSMES participation are even lower in rural populations.

Studies examining barriers to DSMES have identified a variety of reasons for DSMES underutilization including barriers at the health system level, provider level and patient level. One of the fundamental barriers identified by the American Association of Diabetes Educators was lack of a DSMES referral from a provider. Referring a patient to DSMES necessitates clinician awareness and engagement, patient identification, a referral mechanism, and an available DSMES supplier, and barriers can and do occur throughout this process. The ongoing expansion of electronic health records (EHR) creates opportunities to more efficiently and comprehensively identify patients who could benefit from DSMES and supports electronic referral processes. A recent quality improvement study implemented an electronic DSMES referral process to identify and refer patients for DSMES at the four key time points recommended by the ADA, which, in combination with protocol training, increased DSMES referrals from 0% to 31%. The proposed study leverages unique statewide partnerships to implement and expand health information technology to automate patient identification and facilitate referrals to DSMES services. We hypothesize, however, that health information technology is necessary, but not sufficient, to drive DSMES utilization.

Availability of DSMES in Kentucky has increased but utilization remains low. As of 2019, there were 90 nationally recognized and accredited DSMES programs in Kentucky, which provided in-person classes in 80 of Kentucky's 120 counties. Healthy Living with Diabetes, an umbrella DSMES program administered by the Kentucky Department of Public Health (KDPH), is the largest DSMES program in the state. KDPH partners with 17 local health districts across Kentucky to provide free DSMES services in-person in 66 counties and via telehealth to residents in all 120 counties. The number of counties with DSMES services in Kentucky increased from 27 counties in 2012 to 80 counties in 2019. However, during this same period, annual DSMES participation decreased from a high of 14,545 participants in 2013 to 10,278 participants in 2019.

The KDPH DSMES program ameliorates several of the potential barriers, namely geographic access (all counties covered), cost to patient (free), and limited provider reimbursement (diabetes educators are government employees), suggesting that DSMES supply is not the limiting factor in DSMES utilization. Low DSMES demand is likely a larger driver of low DSMES utilization in Kentucky. Prior research found clinician referral to be a significant driver of DSMES uptake, such that strategies that target patient identification, bolster referral mechanisms, and increase clinician engagement and awareness should increase DSMES utilization in Kentucky.

Kentucky suffers from a high prevalence of diabetes and its associated complications. DSMES improves diabetes outcomes and is now widely available to Kentuckians but is vastly underutilized. Clinic and provider-level factors contribute to low DSMES utilization, and the Chronic Care Model provides a blueprint for clinics to identify and address DSMES barriers. Our study team has successfully used the Chronic Care Model to improve diabetes care in rural Kentucky clinics and will use this previous experience to plan, implement, and evaluate an intervention that utilizes health information technology and collaborative practice facilitation to increase DSMES utilization.

This project will yield an evidence-based implementation strategy that is scalable and sustainable and has the potential to reduce diabetes-related morbidity and mortality through efficient, systematic identification and referral of patients with diabetes to accredited and recognized DSMES providers.

Objectives

List your research objectives. Please include a summary of intended research objectives in the box below.

In this study, we propose implementing health information technology, including automated patient identification and bidirectional secure messaging between clinicians and DSMES providers, and using practice facilitation to address referral barriers and increase clinician awareness and motivation. We have partnered with KDPH (statewide DSMES provider), Kentucky Regional Extension Cooperative (KY-REC, practice facilitation partner), Kentucky Health Information Exchange (health information technology (HIT) partner) and two healthcare systems in rural Kentucky. Our proposal builds on a diabetes quality improvement collaborative facilitated by KY-REC and KDPH that demonstrated increased DSMES utilization. We will use a rigorous study design to evaluate implementation processes and effectiveness by testing the hypothesis that patient identification and referral strategies, bidirectional linkages between clinics and DSMES providers, and primary care clinician engagement will increase DSMES utilization through the following objectives:

Objective 1 – Planning: To use an established implementation science framework (PRISM) to identify determinants of DSMES uptake in Kentucky by interviewing previous DSMES quality improvement collaborative stakeholders, and to adapt the previous intervention using implementation mapping to connect stakeholder determinants to intervention strategies and outcomes.

Objective 2 – Implementation: To implement an intervention comprised of health information technology and a practice facilitation collaborative with two healthcare systems in rural Kentucky to increase DSMES referral rates and gather preliminary data for the planned R01 study.

Objective 3 – Evaluation: To evaluate the pragmatic implementability of the intervention by assessing the feasibility, acceptability, and sustainability of the intervention via stakeholder and participant survey, administrative and interview data.

Study Design

Describe and explain the study design (e.g., observational, secondary analysis, single/double blind, parallel, crossover, deception, etc.).

- **Clinical Research:** Indicate whether subjects will be randomized and whether subjects will receive any placebo.
- **Community-Based Participatory Research:** If you are conducting [community-based participatory research \(CBPR\)](#), describe strategies for involvement of community members in the design and implementation of the study, and dissemination of results from the study.
- **Qualitative research:** Indicate ranges where flexibility is needed, if a fixed interview transcript is not available, describe interview topics including the most sensitive potential questions.
- **Research Repositories:** If the purpose of this submission is to establish a Research Repository (bank, registry) and the material you plan to collect is already available from a commercial supplier, clinical lab, or established IRB approved research repository, provide scientific justification for establishing an additional repository collecting duplicate material. Describe the repository design and operating procedures. For relevant information to include, see the [UK Research Biospecimen Bank Guidance](#) or the [UK Research Registry Guidance](#).

Objective 1 involves interviews with key stakeholder and implementation mapping to adapt the previously implemented Diabetes Quality Improvement Learning Collaborative (DLC) for maximal impact on DSMES utilization. We will engage clinical practices that participated in the initial collaborative (conducted by our partners at the Kentucky Regional Extension Cooperative) to learn what worked and where there are opportunities to improve the design and delivery of the DLC. Stakeholder input will inform the implementation mapping process. Key stakeholders we plan to interview include clinicians, clinic staff, and DSMES providers. Interviews will be conducted via phone and audio will be recorded. Guided by the PRISM framework, we will ask questions about the previous DLC implementation as well as hypothetical questions to guide necessary contextual adaptations for future administration. Specifically, we will explore organizational perspectives related to the DLC, characteristics of organizations that impacted/might impact the success of the DLC, ways in which the external environment impacted/might impact intervention success, and infrastructure needs to ensure implementation success. After collecting stakeholder input, we will use implementation mapping to identify objectives, barriers, and implementation determinants. These will then inform the adaptation of the DLC implementation strategies and lead to implementation protocols and evaluation plans. Data collected and synthesized in Objective 1 will refine and adapt this preliminary model for use in Objective 2.

Objective 2 is a pragmatic cluster randomized trial. We have partnered with two rural healthcare systems (one in eastern Kentucky and one in Western Kentucky) for this study. Two clinics from each system will be randomized to participate in the intervention (4 total intervention sites) and the remaining clinics will serve as the control sites. The intervention consists of health information technology (including an automated patient identification system and bidirectional e-referral system connecting clinics to the DSMES providers) and a practice facilitation collaborative. The collaborative is a structured, facilitated process that brings together teams from different organizations to learn from one another. The collaborative utilizes the Model for Improvement, a quality improvement approach designed by the Institute for Healthcare Improvement that uses rapid cycle quality improvement – repeated PDSA (plan do study act) cycles meant to identify care quality barriers and rapidly implement and measure change. Teams from intervention clinics will apply this quality improvement strategy to identify and address quality gaps in diabetes care and DSMES utilization at their clinics. Practice facilitators on the study team will provide individualized coaching (practice facilitation) to clinics in the intervention arm of the study. We will assess the effect of the interventions on DSMES referrals (primary outcome), by comparing rates of referrals between intervention and control clinics (clinics within the healthcare system not randomized to the intervention). Secondary outcomes include DSMES attendance, patient satisfaction and diabetes knowledge, A1c control, and intervention feasibility and acceptability.

Objective 3 involves surveys and interviews with clinic staff that participated in the intervention and DSMES providers from the geographic areas where the intervention took place. Interviews will be conducted via phone and audio will be recorded. The goal of Objective 3 is to understand how the various implementation strategies embedded within the practice facilitation collaborative and clinical context influenced DSMES uptake to inform future refinement for program replication and scale-up.

Attachments

Subject Recruitment Methods & Advertising

Describe how the study team will identify and recruit subjects. Please consider the following items and provide additional information as needed so that the IRB can follow each step of the recruitment process.

- How will the study team identify potential participants?
- Who will first contact the potential subjects, and how?
- Will you use advertisements? If so, how will you distribute those?
- How and where will the research team meet with potential participants?
- If applicable, describe proposed outreach programs for recruiting women, minorities, or disparate populations.
- How you will minimize undue influence in recruitment?
- Attach copies of all recruiting and advertising materials (emails, verbal scripts, flyers, posts, messages, etc.).

For additional information on recruiting and advertising:

- [IRB Application Instructions - Advertisements](#)
- [PI Guide to Identification and Recruitment of Human Subjects for Research](#)

Objective 1: Kentucky Regional Extension Cooperative staff who supported the first Diabetes Learning Collaborative will recruit two stakeholders from each of the five participating clinical practices to participate in surveys and a key informant interview. KDPH will aid in recruiting three DSMES providers from the regions where the first Diabetes Learning Collaborative took place. Recruitment phone and email scripts are attached.

Objective 2: We have partnered with two healthcare organizations in Kentucky for this pilot study: Mercy Health (Mercy Health Marcum & Wallace and Mercy Health Primary Care Clinics (see LOS) and Pikeville Medical Center (see LOS). Both healthcare organizations are non-profit health centers that provide primary and preventive health care to underserved patients. Pikeville includes one participating clinic that is a federally qualified health center. Recruitment for the proposed study targets healthcare organizations in rural settings with multiple clinical sites to allow control and intervention clusters to be randomized at the clinic level within a healthcare organization. This strategy enables us to pilot our intervention in two distinct rural Kentucky settings where the population is disproportionately burdened with diabetes. We will use as control sites other clinics within the healthcare organization with similar patient populations and are of a similar size, location, and financial structure as the intervention site.

Objective 3: Kentucky Regional Extension Cooperative staff will recruit two stakeholders from each of the 11 participating clinical practices from two healthcare systems to participate in surveys and a key informant interview. KDPH will aid in recruiting two DSMES providers from the regions where UP FOR IT took place.

n/a

Attachments

Attach Type	File Name
Advertising	DSMES AIM 1 Recruitment Email_11.1.22.pdf

Research Procedures

Describe how the research will be conducted.

- What experience will study participants have?
- What will study participants be expected to do?
- How long will the study last?
- Outline the schedule and timing of study procedures.
- Provide visit-by-visit listing of all procedures that will take place.
- Identify all procedures that will be carried out with each group of participants.
- Describe deception and debrief procedures if deception is involved.

Differentiate between procedures that involve standard/routine clinical care and those that will be performed specifically for this research project. List medications that are explicitly forbidden or permitted during study participation.

Objective 1: A study team member not involved in the first DLC in will conduct the key informant interviews to minimize stakeholder and interviewer bias. Interview guides are attached. Interviews will happen via telephone and will be recorded; we will transcribe interviews for analysis. Based on these findings, key stakeholders and members of the research team will utilize the PRISM Assessment Tool (attached) a group-based action planning approach, to assess and address contextual domains for the implementation of an evidence-based intervention (DSMES) and select or adapt strategies that address key areas identified as being important and showing low alignment with the local context.

